| Diagnosis and Main Inclusion Criteria | Depressed adolescent (ages 12-18) participants with moderate to severe major depressive disorder (MDD) defined by a score of 40 or greater on the Children’s Depression Rating Scale, Revised (CDRS-R) and an interview with the Mini International Neuropsychiatric Interview (MINI). |
| Study Device | NeuroStar® TMS Therapy System in XPLOR research configuration |

| | |
|--------------------------------|---|
| 
Duration of Exposure
 | 
Phase I - 6 weeks (30 sessions) and 3 week taper (3 sessions for one week, then 2 sessions for the next week, then 1 session for the last week of the taper). Based on randomization participants will either receive sessions of 1 Hz rTMS at 120 % motor threshold (MT) with 2400 continuous pulses or 10 Hz rTMS at 120 % MT with 4 seconds on and 36 seconds off for 2400 pulses. Both 1 Hz and 10 Hz rTMS sessions will be delivered to the left dorsolateral prefrontal cortex (LDLPFC).
 
Phase II- 2 weeks (10 sessions) of continuous theta burst (cTBS) or intermittent theta burst (iTBS) based on biomarker (ICF) status. Note that TBS sessions involve the delivery of 3 pulses of 50 Hz stimulation given every 200 milliseconds (ms) or 5 Hz. Participants assigned to cTBS will receive 10 daily sessions (5 sessions per week for two weeks) with 120 second trains of uninterrupted TBS for 1800 pulses at 80% MT. Participants assigned to iTBS will receive 10 daily sessions (5 sessions per week for two weeks) with 2 second trains every 10 seconds for a total of 570 seconds for 1800 pulses. Both cTBS and iTBS sessions will be delivered to the LDLPFC.
 
NeuroStar TMS is not an implant. Stimulation is delivered during the daily sessions in the neurostimulation suite.
 |
| 
Reference therapy
 | 
Not Applicable
 |

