1.5.3 Potential Benefits

Although the interventional component of the study (randomized biomarker stratified trial of 1 Hz or 10 Hz rTMS and extension trial of cTBS or iTBS for nonresponders) is considered more than minimal risk to adolescents, TMS treatments offer a potential direct benefit for the individual participant.^{33 81,82} Notably all depressed, adolescent participants will received an active form of TMS. There is no placebo or sham condition. In addition, the schedule of mood assessments and daily assessments during the interventional portion of the study for any adverse events has been developed to optimize monitoring the participant's well-being.

Standard TMS dosing (1 Hz and 10 Hz) has been applied more broadly than TBS to children and adolescents in the course of investigational, therapeutic studies.⁸³ The intent for the proposed intermittent theta-burst stimulation (iTBS) and continuous theta-burst (cTBS) exploratory extension trial (Phase II of the proposed study) is to maximize the infrastructure of the proposal for both research participants and our field. Theta burst stimulation (TBS) is an alternative dosing approach in which 3-pulse 50 Hz bursts are delivered at 5 Hz. With iTBS, 2 second trains are delivered to the LDLPFC every 10 seconds for 1800 pulses putatively inducing plasticity changes that resemble long-term potentiation. Continuous theta-burst stimulation (cTBS) delivers 2 second trains of 5 Hz stimulation continuously for 1800 pulses In general it has been speculated that iTBS sessions increase cortical excitability and that cTBS sessions decrease cortical excitability.⁸³⁻⁸⁵

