Participants in Phase I will be stratified based on ICF testing (high or low) at baseline. An ICF of >1.5 at baseline is considered “high” and an ICF ≤ 1.5 is considered “low”. Based on our prior work and review of literature, a sample of depressed adolescents will have an even distribution of high and low ICF values. After stratification, adolescents are randomized to either LDLPFC 1 Hz rTMS with 2400 continuous pulses per session at 120% motor threshold or LDLPFC 10 Hz rTMS with 4 seconds on 36 seconds off for 2400 pulses each session at 120% of resting motor threshold. Hence sessions in each treatment arm with two different types of rTMS (1 Hz and 10 Hz) will have identical intensities (120% motor threshold) durations (40 minutes), number of pulses (2400), and treatment location (LDLPFC). Up to 50 nonresponders in Phase I will be offered to the opportunity to enroll in a Phase II. The decision to enroll in Phase II must be made by the subject no more than 30 days after the last day of Taper Week 3. We will deliver therapeutic rTMS sessions with a Neurostar XPLOR system magnetic stimulator. The research team will localize rTMS treatment sites with the Beam F3 method. Prior research demonstrates that this is a valid and reliable method for scalp location of the dorsolateral prefrontal cortex with comparable results to more expensive, time intensive, MRI-guided approaches.⁸⁷ Our prior research demonstrates that the Beam F3 method is a feasible and reliable method for rTMS treatment localization in adolescents.⁶⁹ Efficacy measures (CDRS-R) and TMS biomarkers will be collected at baseline and weekly. The TMS biomarker panel includes ICF, Motor threshold (MT) Short-interval intracortical inhibition (SICI), long-interval intracortical inhibition (LICI), and cortical silent period (CSP).

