Participants in Phase II will be assigned to 2 weeks of cTBS if their intracortical facilitation measure (baseline assessment for TBS extension trial) is >1.5 . Participants will be assigned to 2 weeks of iTBS if their ICF (baseline assessment for TBS extension trial) is ≤ 1.5 . Extension trial TBS will be applied to the LDLPFC with the Beam F3 method. Participants receiving cTBS will receive 10 daily (5 sessions per week for two weeks) 120 second trains of uninterrupted TBS for 1800 pulses at 80% motor threshold. Participants receiving iTBS will receive 10 daily (5 sessions per week for two weeks) 2 second trains every 10 seconds for a total of 570 seconds for 1800 pulses at 80% motor threshold. Efficacy measures (CDRS-R) and TMS biomarkers will be collected at baseline, 1 week, and 2 weeks. The TMS biomarker panel includes ICF, Motor

threshold (MT) Short-interval intracortical inhibition (SICI), long-interval intracortical inhibition (LICI), and cortical silent period (CSP).

Safety Precautions for Seizures and Cardiogenic Syncope during Phase I and Phase II TMS sessions.

We will follow our standard lab procedures for screening to minimize the risk of seizures and syncope, monitoring during treatment sessions, and immediately addressing any induced seizures or syncope during TMS sessions.

With regard to the potential for seizures, all patients will be carefully screened for current or historical factors that may increase the risk of seizures (see Exclusion criteria). The Transcranial Magnetic Stimulation Adult Safety Screen (TASS) will be used to specifically query for any potential seizure or syncope risks. Neurologic disease which may increase the risk for seizures is part of the exclusion criteria.^{74,75} Patients undergoing TMS in the proposed study will not be taking medications which could potentially lower their seizure threshold. All TMS sessions will be supervised by a physician located in the treatment suite and all personnel involved will be provided with training in the identification of potential prodromal signs or symptoms of a seizure, particularly the identification of more subtle behavioral events which may herald the occurrence of a frontal lobe seizure, such as changes in level of consciousness or inattention.

All TMS sessions will be conducted in the neurostimulation suite with access (within minutes) to medical facilities and life-support equipment in the event a seizure should occur.

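### The iTBS pulse total, train interval and session duration cannot all hold: 570 seconds at one train per 10 seconds gives 1710 pulses, not 1800

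*Combined protocol and SAP*

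**What the plan says.** The iTBS session is fully specified in two places. Section 5.3 (Treatment, Phase II) has participants receive, on each of 10 daily sessions, "2 second trains every 10 seconds for a total of 570 seconds for 1800 pulses at 80% motor threshold". The Study Summary, under Duration of Exposure, gives "2 second trains every 10 seconds for a total of 570 seconds for 1800 pulses". Section 1.5.3 repeats the train length, interval and pulse total without a duration: "2 second trains are delivered to the LDLPFC every 10 seconds for 1800 pulses".

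The burst structure is stated twice and consistently. The Study Summary says "TBS sessions involve the delivery of 3 pulses of 50 Hz stimulation given every 200 milliseconds (ms) or 5 Hz", and Section 1.5.3 says "3-pulse 50 Hz bursts are delivered at 5 Hz".

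Two other patterned regimens in Section 5.3 serve as checks. They are cTBS, given as "120 second trains of uninterrupted TBS for 1800 pulses at 80% motor threshold", and the Phase I arm, given as "10 Hz rTMS with 4 seconds on 36 seconds off for 2400 pulses each session", for which the same section states a 40-minute session.

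No section gives a number of iTBS trains or an interval other than 10 seconds.

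**The concern.** Once the burst structure and train length are fixed, any two of pulse total, train interval and session duration determine the third. Here all three are stated, and they do not agree.

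These are operative treatment parameters, not background text. The note under Table 4 requires two staff members to complete a checklist before every Phase II treatment, so that sessions are delivered accurately. Staff cannot confirm a session against three values when no session can satisfy them all. Section 1.5.3 also presents Phase II as a source of pilot data for later grant applications, so the regimen needs to be reportable and reproducible from the protocol.

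**Working it through.** **Inputs**

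- Burst: 3 pulses, one burst every 200 ms, i.e. 5 per second (Study Summary; Section 1.5.3).
- iTBS: 2 s trains, every 10 s, 570 s, 1800 pulses (Study Summary; Section 5.3).
- cTBS: 120 s uninterrupted, 1800 pulses (Section 5.3).
- 10 Hz: 4 s on, 36 s off, 2400 pulses, 40 minutes (Section 5.3).

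**Checking the method on the other regimens**

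- Pulse rate within theta burst: 3 × 5 = 15 pulses per second.
- cTBS: 120 s × 15 = 1800 pulses. This matches the protocol.
- 10 Hz: each train is 4 s × 10 = 40 pulses; 2400 / 40 = 60 trains; 60 × (4 + 36) s = 2400 s = 40 minutes. This matches the protocol.

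**Applying it to iTBS**

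- Pulses per train: 15 × 2 s = 30.
- Trains that finish within 570 s, starting at 0, 10, ..., 560 s: 57.
- Pulses in 570 s: 57 × 30 = 1710, against 1800 stated. The shortfall is 90, and 90 / 1800 = 5.0%.
- Over 10 sessions: 17,100 against 18,000.

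**Working back from 1800 pulses**

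- Trains needed: 1800 / 30 = 60.
- Time to the end of the last train: 59 × 10 + 2 = 592 s. That is 22 s over, and 22 / 570 = 3.9%.
- Counted as 60 full cycles: 60 × 10 = 600 s, which is 30 s over (5.3%).

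**Other readings of the interval and duration**

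| Reading | Trains | Pulses | Against 1800 |
|---|---|---|---|
| 10 s from onset to onset, complete trains only | 57 | 1710 | −5.0% |
| As above, plus a train starting at 570 s and ending at 572 s | 58 | 1740 | −3.3% |
| 10 s pause after each train (12 s cycle) | 48 | 1440 | −20.0% |

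For the last row, the 48th train ends at 47 × 12 + 2 = 566 s, and the next would start at 576 s.

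**Interval that would fit**

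Sixty trains fit in 570 s with a cycle of 570 / 60 = 9.5 s (full cycles), or (570 − 2) / 59 = 9.63 s (ending with the last train). Neither is the stated 10 s.

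**The case against.** The best case on the other side accepts the arithmetic and disputes its consequences. Much of that case stands.

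- **The pulse number may be unaffected.** If delivery is governed by train interval and pulse count, each session delivers 1800 pulses and only the elapsed time departs from the text, by about 22 s. Section 1.5.3 gives exactly those two values with no duration, and they do not conflict. A reader might infer that iTBS participants will be under-dosed. The documents do not support that as a certainty.
- **How the device is set is not stated.** Section 5.3 refers administration to the manufacturer's user manual and training material. No section says which parameters are entered, so nothing can be concluded about what the device must be given.
- **Overdose reporting.** A reader might link the inconsistency to the rule in Section 5.7 that treats excess pulses as a reportable overdose. That rule names only 2400, the Phase I count, in a paragraph about the 6-week course. The stated iTBS total is 1800 wherever it appears, and 1710 lies below it, so the arithmetic does not point to an excess over any stated count.
- **Matching to cTBS.** Both Phase II regimens list 1800 pulses, and a reader might infer deliberate matching. The protocol claims matched sessions only for 1 Hz and 10 Hz in Phase I. Phase II assignment is by ICF, not by randomisation.
- **Safeguards exist.** Besides the daily checklist, Section 9.4 has treatment parameters retained by the device software and summarised daily in the source document. These should make the delivered dose recoverable, though they do not repair the specification.

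None of this reconciles the three figures. The same method reproduces the cTBS and 10 Hz sessions exactly, 570 seconds is not marked as approximate, and it appears identically in two places, so loose rounding is an unlikely explanation.

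**Conclusion.** The iTBS session is internally inconsistent as written. With 30 pulses per train, the stated interval and duration give 1710 pulses (5% below the stated total), while the stated interval and pulse total need 592 s (about 4% longer). The 1710 figure assumes that the 10 seconds run from train onset to train onset and that only complete trains count. The alternatives give 1740 or 1440, so the finding of inconsistency does not depend on the reading.

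Which quantity departs from the text in practice depends on which values govern delivery, and the documents do not say.

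The reach is small. Phase II is exploratory and capped at 50 participants, and only those with ICF at or below 1.5 receive iTBS. Section 7 specifies no Phase II analysis, and nothing in the Phase I primary analysis is affected. It still merits correction because these are live treatment parameters that staff are asked to verify each day.

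**What to change.** Reconcile pulse number, train interval and session duration for iTBS so that all three agree in the Study Summary (Duration of Exposure) and in Section 5.3, and keep Section 1.5.3 in line. Stating the number of trains and whether the interval runs from onset to onset would remove the remaining ambiguity. Confirm the agreed values against the programmed device setting and the Phase II pre-treatment checklist. Which value is correct is for the sponsor to decide.

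The cost is a wording correction in two places plus a check of the third. If the reconciliation changes a delivered parameter and not just its description, the sponsor should consider whether the FDA and IRB notification provision in Section 8.3.3 applies. No sample size or analysis has to change.

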5.4 Packaging and Labeling

The NeuroStar XPLOR[®] Therapy System will be clearly labeled with the following warning:

“CAUTION – Investigational Device. Limited by Federal (or United States) law to investigational use”

5.5 Blinding of Study

In both phases of the study (phase I and phase II) participants and study team members completing clinical rating scales (Drs. [name], [name], or other designated and trained clinical raters) will be blinded to treatment assignment. The study team member completing clinical rating scales will not be allowed in the treatment suite during therapeutic rTMS sessions (10 Hz, 1 Hz, iTBS, or cTBS). We will recruit adolescent participants with no prior TMS exposure or experience and maintain blind to rTMS treatment assignment (1 Hz or 10 Hz for phase I and cTBS or iTBS for phase II). A pre-post treatment expectancy and experience form will ask that participants and parents guess which treatment (1 Hz, 10 Hz, iTBS, or cTBS) was received.⁸⁸

5.6 Receiving, Storage, Distribution and Return

5.6.1 Receipt of Investigational Devices

NeuroStar XPLOR[®] TMS Therapy System will be delivered to the Principal Investigator/Sponsor and installed by Neuronetics.

Upon receipt of the NeuroStar and study treatment supplies, an inventory will be performed and a device accountability log completed by designated study staff. The designated study staff will

count and verify that the shipment contains all the items noted in the shipping invoice. Any discrepancies or damaged or unusable devices in a given shipment will be documented in the device accountability log. The Investigator at each study site will notify Neuronetics immediately of any discrepancies or damaged or unusable products.

5.6.2 Storage

The supplies and disposables required for each treatment will be stored in a supply station separate from clinical practice stock at each site.

5.6.3 Distribution of Study Device

All participants will be treated using a new single-use treatment disposable, or SenStar[®] Treatment Link, from their treatment site at the start of every new treatment. The treatment packs and SenStar Treatment Links will be stored in an area that is separate from clinical practice stock. Regular reconciliation of SenStar Treatment Links received from Neuronetics, SenStars used during study treatments, and SenStars remaining will be performed. This reconciliation of the inventory will be logged in the Device Accountability Log, signed, and dated. Any discrepancies noted will be documented, Neuronetics will be notified, and an investigation will be conducted to determine the cause of the discrepancy. Any SenStars disposed of for any reason other than use for the study will be documented in the Device Accountability Log at the time of disposal.

5.6.4 Return or Destruction of Study Device

NeuroStar devices and/or XPLORs that are loaned to the study site for purposes of this study will be returned to Neuronetics at conclusion of the study by Neuronetics personnel. SenStars[®] that are remaining in the site study research inventory at the completion of the study will be packaged and returned to Neuronetics.

5.7 Participant Compliance Monitoring

Non-adherence to the assigned treatment regimen is defined as missing ≥ 3 treatments in daily sequence, or missing more than 20% of the total number of treatment sessions occurring during the 6 weeks of acute treatment (does not include taper treatments) as outlined in the schedule of events (i.e., 100% compliance = 30 total treatments). However, if the participant does miss a treatment, the participant must not go more than 3 calendar days without a treatment session. Treatments missed during the taper visits are considered protocol deviations. Participants who are unable to comply with this schedule may be withdrawn from the investigational treatment portion of the study. If a participant receives more than the prescribed number of pulses (i.e. 2400 pulses of good contact), this would be considered an overdose and documented on the SAE form and reported to the IRB and US FDA.

5.8 Prior and Concomitant Therapy

5.8.1 Documenting Prior and Concomitant Therapy

Reasonable efforts will be made to determine all somatic therapies for depression received by the participant in the past 2 years. All other medications and therapies received within six months of study enrollment will also be determined. All relevant information will be recorded on the Participants CRF. The antidepressant treatment history form (ATHF) will be completed to quantify treatment history.

5.8.2 Permitted Concomitant Therapy

Zaleplon, zolpidem, or zopiclone (1 dose nightly) as needed for treatment emergent insomnia or lorazepam (up to 2 mg daily) for treatment emergent anxiety, may be administered for up to 14 doses during Phase I and an additional 5 doses during Phase II. The use of alternative hypnotics or anxiolytic compounds requires prior approval from the PI/Sponsor ([name]). Hormonal contraceptives are allowed if the participant has been on a stable dose for at least 3 months. Short-term treatments for headaches, allergies, colds, and flu symptoms will be allowed during the study provided the medications utilized have no established psychotropic effects that would be expected to confound interpretation of study outcome measures. These medications may include non-sedating, over-the-counter, or prescription antihistamines, analgesics and decongestants. All questions regarding the acceptability of specific medications must be approved by the PI/Sponsor ([name]). Please see appendix A for further information.

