Imbalances in GABAergic and glutamatergic tone play a key role in depression,^{13,14} pathophysiologic stress responses,¹⁵ and emotional numbing or anhedonia found in behavioral manifestations of the negative valence system.¹⁶ These GABAergic and glutamatergic imbalances have differential causes, effects, and behavioral manifestations in adolescents as compared to adults.¹⁷⁻¹⁹ For example, recent preclinical work has demonstrated that repeated stress in adolescent rats inhibits GABAergic projections to the amygdala thereby impairing regulatory neurocircuitry.²⁰ In adult rats, chronic stress facilitates glutamatergic excitatory neurotransmission with ensuing effects on the lateral nucleus of the amygdala, hippocampus, and frontal cortex.²¹⁻²³ Developmental differences in frontolimbic GABAergic and glutamatergic tone may underlie variances in adolescent depressive symptom presentations and treatment responsiveness.^{20,24,25} A deeper understanding of frontolimbic GABAergic and glutamatergic tone in adolescent depression would assist with precision medicine approaches and intervention development. Certain types of transcranial magnetic stimulation (TMS) provide noninvasive measures of cortical GABAergic and glutamatergic tone.²⁶⁻²⁸ There are different types of TMS. Repetitive TMS (rTMS) delivers multiple pulses per session over many days or weeks for therapeutic purposes. The effects of rTMS can also be studied as a probe of brain function. Theta burst stimulation (TBS) is a form of rTMS that is thought to have more rapid effects on synaptic plasticity and clinical symptoms than standard rTMS. Single and paired-pulse TMS paradigms are used to study the physiology of the brain. Neurophysiological measures collected with transcranial magnetic stimulation (TMS) such as intracortical facilitation (ICF), short-interval intracortical inhibition (SICI), long-interval intracortical inhibition (LICI), and the

cortical silent period (CSP) are noninvasive measures of cortical GABAergic and glutamatergic tone.²⁸⁻³¹

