5.6.3 Prohibited Concomitant Therapy

Any medication administered for the treatment of any psychiatric or neurologic disorder or any other known CNS active drugs, including herbal, over-the-counter, and homeopathic medications, MAOIs, other antidepressants, antipsychotics, stimulants and mood stabilizers are prohibited during this study (See Appendix A, Concomitant Medication Exclusion List). Use of Zaleplon, zolpidem, zopiclone or lorazepam for more than the permitted days (see above) or beginning a new regimen of hormonal contraception may lead to excluding the participant from the study.

6 Study Procedures

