MIXED procedures (mixed model approach) in SAS software will make use of all available data from all participants from the efficacy analysis set, and provide a robust mechanism for handling data that are assumed missing at random (see sensitivity analysis section below for MNAR).

Secondary Aim

Data Analysis Plan for Secondary Aim 2 (Hypotheses 2a–2d)

Secondary Continuous Outcome: Intracortical Facilitation (ICF)

Intracortical Facilitation over the 6-week study period will be the secondary continuous outcome measure. A within-Participants linear mixed model analysis of repeated measures will be used to examine the change in ICF over 6 weeks of rTMS treatment in depressed adolescents. We will consider the inclusion of pubertal state and treatment resistance (as defined by ATHF score) during the study period as a covariate in the mixed model. A mixed model analysis will be conducted on ICF for those who receive 6 weeks of low frequency (1 Hz) rTMS treatment (Hypothesis 2a) and, in a separate model, for those who receive 6 weeks of high frequency (10 Hz) rTMS treatment (Hypothesis 2c). Restricted maximum likelihood estimation, Type 3 tests of fixed effects, and generalized least squares (LS) will be used, with the Kenward-Roger correction applied to the appropriate and best fitting covariance structure. The sandwich (robust covariance matrix) estimator will also be considered. LS mean contrasts (between ICF measurement time periods) from the mixed model will also be examined. A separate linear mixed model analysis similar to that described above will also be implemented over 6 weeks of acute rTMS treatment and throughout the 6-month follow-up period. A nonlinear mixed model will be considered (e.g., exponential decay/growth model) to estimate ICF over the 6 weeks of rTMS treatment (if the pattern of ICF values suggests that a nonlinear model is deemed necessary).

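### As-needed hypnotics or lorazepam are allowed during Phase I, but nothing separates a dose from the weekly ICF reading and no Aim 2 or Aim 3b analysis uses the dose record

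*Combined protocol and SAP*

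**What the plan says.** Section 5.8.2 allows "Zaleplon, zolpidem, or zopiclone (1 dose nightly) as needed for treatment emergent insomnia", and continues that "lorazepam (up to 2 mg daily) for treatment emergent anxiety, may be administered for up to 14 doses during Phase I". The cap covers the hypnotics as well as lorazepam, and 5 further doses are allowed in Phase II. The same section admits short-term remedies for headache, allergy, cold and flu only if they have "no established psychotropic effects that would be expected to confound interpretation of study outcome measures". It applies no such test to the hypnotics or lorazepam, although Appendix A lists them under psychotherapeutic agents.

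The section on prohibited therapy (numbered 5.6.3) deals only with overuse. It warns of possible exclusion for "Use of Zaleplon, zolpidem, zopiclone or lorazepam for more than the permitted days (see above", counting days where section 5.8.2 counts doses. The notes to Table 3 and Appendix A refer back to the allowance and add no timing rule.

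On the measures, section 1.1 says that ICF and the other TMS readings "are noninvasive measures of cortical GABAergic and glutamatergic tone". Section 7.2 states that "Intracortical Facilitation over the 6-week study period will be the secondary continuous outcome measure". Table 3 schedules the reading at baseline and in each of Weeks 1 to 6. The ICF procedure (section 5.2 and Appendix B) and the MRS procedure (section 3.1) do not mention medication. Concomitant treatment is recorded throughout Phase I (Table 3) and daily in Phase II (Table 4).

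**The concern.** Section 4.2 excludes concurrent psychotropic medication at entry, and the allowance covers only symptoms that emerge on treatment. Exposure to these drugs therefore falls after baseline, inside the change that is analysed.

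Section 7.2 tests that change in separate models for the 1 Hz and 10 Hz groups: ICF for Aim 2, GABA and Gln/Glu for Aim 3b. A within-arm test has no concurrent comparator, so equal use in both arms would not cancel. The model of ICF on CDRS-R has a further weakness. Anxiety or insomnia prompts a dose and may itself track depression severity, so a dose could link the two measures without any action of rTMS.

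At stake is the interpretation of the secondary endpoint and, less directly, of Aim 3b. A change caused wholly or partly by a recent dose would be read as the effect of a stimulation frequency. The primary CDRS-R interaction is not the subject of this point.

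**Working it through.** The documents state no figure on this point, so there is none to reproduce. The check has three parts.

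**1. Is there a rule or an adjustment anywhere?**
- Medication sections (4.2, 4.4.1, 5.8.2, Prohibited Concomitant Therapy, Table 3 notes, Appendix A): a cap and a consequence for overuse, but no interval before a reading.
- Measurement sections (3.1, 5.2, 5.3, 6.1 to 6.3, Appendix B): no instruction to postpone a reading or to note the time of the last dose.
- Analysis (7.2): Aim 2 considers pubertal state and treatment resistance as covariates; Aim 3 names none. The sensitivity section covers missing data only.

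**2. Does the cap protect the readings?**
Inputs: 14 doses (section 5.8.2); six weekly readings, 42 treatment days, and 63 days with the taper (Table 3). Fourteen exceeds six, so every weekly reading could follow a dose within the allowance. Assume full use, one dose per day, on random days:
- Expected readings after a dose = 6 × 14 / days. Over 42 days this is 2.0; over 63 days it is 1.3.
- Chance of at least one = 1 − C(days − 6, 14) / C(days, 14). Over 42 days this is 1 − 0.072 = 0.928; over 63 days it is 1 − 0.206 = 0.794.

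These figures describe a full user. The proportion of participants who use the drugs is not given.

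**3. How large could the effect on a within-arm test be?**
This part is illustration. Section 7.1 plans 100 evaluable participants, so about 50 per arm, with two-sided alpha 0.05. For a single change contrast, the change detectable with 80% power is (1.960 + 0.842) / √50 = 0.40 SD of change.

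Let p be the share dosed before the reading and s the shift caused by a dose, in SD of change. The spurious mean shift is b = p × s. With no rTMS effect and the SD taken as unchanged, the chance of a significant result is Φ(b√50 − 1.96) + Φ(−b√50 − 1.96).

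| p (assumed) | s (assumed) | b | Chance of significance |
|---|---|---|---|
| 10% | 0.2 | 0.02 | 5.2% |
| 25% | 0.5 | 0.125 | 14.3% |
| 50% | 0.8 | 0.40 | 80.7% |

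Both p and s are assumptions. The range runs from negligible to serious, and the documents do not narrow it.

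**The case against.** The strongest reply is that the drug effect itself is nowhere in the documents. No section says that these drugs shift ICF or MRS, or that an effect would last until the next reading, and the Study Summary and section 2 describe ICF as a glutamatergic measure. This stands. The documents support saying that readings can reflect a recent dose; a reader might infer that they do, and the documents do not support that.

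A reader might also infer that use will be heavier in the 10 Hz arm, because section 1.1 expects advantages in tolerability for 1 Hz. That passage is general and partly about right-sided stimulation, whereas this trial stimulates the left. Nothing links frequency to emergent insomnia or anxiety. Unequal use is speculative, and the within-arm problem does not need it.

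The MRS scan and the Phase II assignment are less exposed. Section 3.1 puts the second scan in the two months after Phase I treatments and assessments end, when the Phase I allowance may have lapsed, though Table 3 marks Week 6. The ICF that assigns Phase II treatment is a new baseline, before any Phase II dose and possibly long after the last Phase I dose.

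It is also fair that the allowance is a deliberate, capped exception, not a contradiction of the test applied to cold and headache remedies. Use is recorded, so exposed readings could be partly identified later. But recording a drug is not the same as recording the time since the last dose, and no planned analysis uses either. Finally, only secondary and exploratory aims are touched, in a study that section 7.1 describes as partly a proof of concept. That limits the weight of the point without removing it.

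**Conclusion.** The gap holds: there is no separation between a dose and the weekly ICF reading, and no Aim 2 or Aim 3b analysis uses the dose record. Because exposure begins after baseline and the tests are within arm, randomisation does not remove it.

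The only size that can be tied to the documents is opportunity for exposure: 1.3 to 2.0 of six readings for a participant who uses the full allowance on separate random days, with a 79% to 93% chance of at least one. Lighter use, or several doses on one day, would lower these figures. Bias in the ICF result also depends on a usage rate and a drug effect that are not given.

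This is an inexpensive improvement that protects the secondary endpoint. It does not show that the ICF or MRS results will be invalid.

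**What to change.** - At each TMS-neurophysiology and MRS visit, record the drug, amount, date and time of the last dose.
- Where possible, if a dose was recently taken, take the weekly ICF reading on another treatment day that week. Table 3 fixes the week of this reading, not the day.
- Keep all readings in the main Aim 2 and Aim 3b analyses. Dropping exposed readings there would select on use after randomisation and remove readings from participants with emergent anxiety or insomnia.
- Before unblinding, prespecify a sensitivity analysis that excludes, or adjusts for, readings within a stated interval of a dose.
- Tabulate use by arm.
- Reconcile the count of doses in section 5.8.2 with the count of days in the section on prohibited therapy.

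The cost is one line on the case report form, SAP wording, minor rescheduling, and some loss of readings in the sensitivity analysis only. For a full user that loss could average about two of six readings. No change to permitted medication is proposed.
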